4.4.2. Safety Population

The Safety Population includes all randomized subjects who receive at least 1 dose of IMP and will be used for all the safety analyses which will be based on the actual treatment received at the double-blind treatment phase.

4.4.3. Open-label Safety Population

The Open-label Safety Population includes subjects who continue into open-label extension phase and receive at least one dose of IMP during the open-label extension phase. The Open-label Safety Population will be used for all the safety and efficacy analyses for open-label extension phase and will be based on the actual treatment sequences received during the overall study phase (Acthar/Acthar or Placebo/Acthar) and total.

5. Subject Disposition

A summary of analysis populations will be presented by treatment group and total for all randomized subjects, the mITT population, the safety population, and open-label safety population. Summary of subject disposition will be presented for double-blind treatment phase and open-label extension phase separately.

Disposition of all randomized subjects in double-blind treatment phase will be summarized by treatment group and total descriptively, including summaries of the number and percentage of subjects who completed the double-blind treatment phase, subjects who continued into the open-label extension phase, subjects who early terminated from the double-blind treatment phase and the reasons for early termination from the double-blind treatment.

In addition, disposition of subjects participating in the optional open-label extension phase will be summarized by actual treatment sequences and total descriptively, including summaries of the number and percentage of subjects who completed the double-blind treatment phase, subjects who continued into the open-label extension phase, subjects who completed the open-label extension phase, and subjects who early terminated from the open-label extension phase. The reasons for early termination from the open-label extension will also be summarized.

The reasons for early termination from the double-blind treatment and the reasons for early termination from the open label extension will be summarized based on the following categories:

- Adverse event
- Death
- Lack of efficacy
- Lost to follow-up
- Met withdrawal criteria
- Non-compliance with study drug
- Physician decision
- Protocol violation
- Study terminated by sponsor

- Withdrawal by subject
- Other

Subject disposition for all randomized subjects and subject disposition for open-label safety population will be provided in by-subject listing, respectively.

6. Protocol Deviations

The significant protocol deviations will be summarized by category using frequency tabulations based on the safety population in the double-blind treatment phase and on open-label safety population in the open-label extension phase separately. The cut off of two study phases has been defined in reporting conventions [section 4.3](#). Listings of significant protocol deviations will be provided to support the summary tables.

7. Demographics and Baseline Characteristics

Demographics and baseline characteristics will be summarized by treatment group and total using the mITT population and safety population in the double-blind treatment phase and open-label safety population in the open-label extension phase. Individual subject listings will be provided to support the summary tables for all randomized subjects in the double-blind phase.

7.1. Demographics

Descriptive statistics will be provided for the following continuous variables collected at baseline:

- Age (year)
- Weight (kg)
- Height (cm)
- Body Mass Index (BMI) (kg/m^2) as recorded on the electronic case report form (eCRF)

The number and percentage of subjects will be provided for the following categorical variables:

- Sex (Male, Female)

- Race (American Indian or Alaska Native, Asian, Black or African American, Native Hawaiian or Other Pacific Islander, White, Multiple, Other)
- Ethnicity (Hispanic or Latino, Not Hispanic or Latino, Unknown, Unreported)
- Female Fertility Status (Surgically Sterile, Post-Menopausal, Childbearing potential)

A female fertility status listing will be provided for all randomized subjects.

7.2. Baseline Disease Characteristics

The following baseline disease characteristics and disease history will be summarized:

- Smoking history (Current Smoker; Ever Smoked, and Never Smoked)
- Current Employment Status (Full Time, Part Time, Retired, Home Maker, and Not Employed)
- Ever Employed/Worked (Yes, No)
- Organs involved in sarcoidosis (A subject may have more than one organ involved in sarcoidosis. The subject will be counted for each organ.)
- Occupational History (Exposure to Mold, Bacteria or Other Microbial Contaminants, Fumes, Asbestos, Wood Burning Smoke, Insecticide, Silicates, Metal Dust or Inorganic Dust, Aerosols, Inorganic Particulate, and Other) and duration of exposure to each type in years
- Time from sarcoidosis diagnosis (months)

Time from sarcoidosis diagnosis in months will be calculated as:

(date of screening - date of sarcoidosis diagnosis + 1)/30.4375.

Sarcoidosis history, smoking history and occupational history data for all randomized subjects will be provided in listings.

Disease characteristics for the subjects who enrolled in the open-label extension phase may be summarized using open-label safety population.

7.3. Medical and Surgical History

Medical and surgical history will be summarized by system organ class (SOC) and preferred term (PT) for the safety population. A subject will be counted only once within

each level of SOC and PT. Percentages are based on the number of subjects within each treatment group. SOC will be presented alphabetically and PTs within each SOC will be presented in decreasing order of frequency calculated based on the Acthar treatment group. Medical and surgical history data for all randomized subjects will be presented in a listing.

8. Treatments and Medications

Study treatments, medications and sarcoidosis specific medications will be summarized by treatment group and total based on the safety population in double-blind treatment phase and then open-label safety population in the open-label extension phase, respectively. Descriptive statistics will be provided for continuous variables and frequency counts and percentages will be applied to categorical variables. Missing or partially missing start/stop dates for prior/concomitant medications will be imputed in order to justify prior/concomitant status, refer to Appendix [15.1.2](#) for imputation details.

8.1. Prior and Concomitant Medications

All prior and concomitant medications will be coded using the WHO Drug dictionary. Prior medications are defined as all non-study medications that were started before the start of the study treatment and either ended before the start of the study treatment or continued into the study treatment period.

Concomitant medications in the double-blind treatment phase are non-study medications that are ongoing during the double-blind treatment phase or with a start date occurring before the first dose of IMP in the open label extension phase.

Concomitant medications in the open-label extension phase are non-study medications that are ongoing during the open-label extension phase or with a start date occurring on or after the first dose of IMP at the open label extension phase.

Medications initiated prior to the first dose of IMP at the open-label extension phase and were continued into the open-label phase will be counted into both phases.

Prior and concomitant medications will be summarized separately. Concomitant medications will be summarized by the double-blind and the open-label phase separately. The tables will present the number and percentage of subjects by WHO ATC level 2 and preferred drug name for each treatment group and total. ATC level 2 will be presented alphabetically, while preferred drug name within each ATC level 2 will be presented in decreasing order of frequency calculated based on the Acthar treatment group. In addition,

the number and percentage of subjects receiving at least one prior or concomitant medication will be presented. A subject with multiple occurrences of a drug class or drug is counted only once in the ATC 2 level or preferred drug name, respectively.

All prior and concomitant medications for safety population will be presented in listings by study phases.

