10. PRIOR AND CONCOMITANT MEDICATION

The start and stop date, dose, unit, frequency, route of administration, and indication for all prior (taken within the 30 days prior to the screening visit) and concomitant (taken from the screening visit through the Follow-up Visit) medications and nondrug therapies (eg, blood transfusions, oxygen supplementation) received will be recorded.

In addition, all prior treatments for sarcoidosis administered since diagnosis will be recorded with start and stop date, dose, unit, frequency and route of administration to the extent of data availability.

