8.2. Prior and Concomitant Sarcoidosis Medications

The prior and concomitant sarcoidosis medications will be summarized by preferred drug name for each treatment group and total. Concomitant sarcoidosis medications will be summarized by the double-blind and the open-label phase, respectively.

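### SAP 8.1 counts drugs stopped before the first double-blind dose as double-blind concomitant for extension entrants, because its second condition has no lower bound and no stop-date test

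*SAP*

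**What the plan says.** SAP 8.1 gives the double-blind rule in two parts joined by an or. The first part is use during the phase: "Concomitant medications in the double-blind treatment phase are non-study medications that are ongoing during the double-blind treatment phase". The second part is a start-date test alone: "or with a start date occurring before the first dose of IMP in the open label extension phase".

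The same section defines prior medications as those started before study treatment that "either ended before the start of the study treatment or continued into the study treatment period", and adds: "Prior and concomitant medications will be summarized separately". Its rule for the extension has the same two-part form, but there the start-date test has a lower bound: "or with a start date occurring on or after the first dose of IMP at the open label extension phase".

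SAP 8.2 applies the prior and concomitant labels to sarcoidosis drugs without redefining them: "Concomitant sarcoidosis medications will be summarized by the double-blind and the open-label phase, respectively". Protocol section 10 describes concomitant by use, not by start date: "concomitant (taken from the screening visit through the Follow-up Visit) medications". It also requires that "all prior treatments for sarcoidosis administered since diagnosis will be recorded", with start and stop dates as far as they are available.

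**The concern.** Every drug begun before the study began before the extension. Read as written, the start-date test therefore admits drugs the subject had already stopped taking, and the double-blind concomitant table mixes past use with current use.

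The sarcoidosis table is where this would show most, because that history goes back to diagnosis. Anti-TNF treatment is the clearest example. A course that ended more than 3 months before screening does not exclude a subject (Protocol 9.2, criterion 7), whereas anti-TNF use during the study is prohibited (Protocol 10.2). Under the literal rule a permitted past course would appear in the double-blind table as if it were on-study use. What is at stake is the description of background therapy by arm.

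**Working it through.** The plan states no figure on this point, so there is nothing to reproduce. The check applies the rule to drug histories and compares it with a corrected rule.

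**Inputs.** Day 1 is the first double-blind dose (SAP 4.3). The first open-label dose is set at day 170, an illustrative assumption close to 24 weeks (24 × 7 = 168 days). The rules are:

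- Literal rule (SAP 8.1): ongoing in double-blind OR start < 170.
- Corrected rule: ongoing in double-blind AND start < 170.

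**Subject who enters the extension:**

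| Drug taken (days) | Prior | Ongoing in double-blind | Start < 170 | Literal: concomitant | Corrected: concomitant |
|---|---|---|---|---|---|
| −2000 to −1000 | yes | no | yes | **yes** | **no** |
| −40 to −10 | yes | no | yes | **yes** | **no** |
| −40 to 50 | yes | yes | yes | yes | yes |
| −40, continuing | yes | yes | yes | yes | yes |
| 20 to 60 | no | yes | yes | yes | yes |
| 100, continuing | no | yes | yes | yes | yes |
| 200 to 230 | no | no | no | no | no |

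Only the first two rows change. The third and fourth are prior drugs that continue into treatment; they belong in both tables under either rule.

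**Grid check.** Start days ran from −60 to 336 in steps of 2, with stop days from the start day to 338 in steps of 2. The two rules disagree in 496 combinations, and in all 496 the drug stopped before Day 1. The count follows directly: 31 start days (−60 to 0), each paired with every stop day from itself to 0, give 31 × 32 / 2 = 496. This is a property of the grid, not an estimate of how many drugs are affected. Keeping the or and adding a Day 1 lower bound to the start-date test gives the same classification as the corrected rule at every grid point.

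**Subject who does not enter the extension.** There is no first open-label dose, so the start-date test cannot be evaluated. If it is taken as not met, a drug stopped before Day 1 is left out; if it is taken as always met, that drug is included. SAP 4.3 places these subjects in the double-blind summaries only and does not say which reading applies. One table could therefore treat entrants and non-entrants differently.

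**Other sections.** SAP 4.3, 8.2 and 15.1.2 contain nothing that removes drugs stopped before Day 1 from the double-blind concomitant table.

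**Size per subject.** SAP 4.1 reports 55 randomised. Arm sizes are not given; under 1:1 allocation about 27 or 28 per arm is assumed. One misplaced subject moves that arm's percentage for a drug by 100 / 27.5 ≈ 3.6 points. How many subjects have such histories cannot be known from the documents.

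**The case against.** The strongest reply is that the intended meaning is clear from context. SAP 8.1 classes drugs that ended before treatment as prior and separates the two tables. SAP section 8 imputes both start and stop dates in order to settle prior or concomitant status, which would be pointless if stop dates played no part. A programmer would probably supply the missing bound, and the planned listings, together with the recorded start and stop dates, would let a reader check old courses. This shows what was meant. It does not change what the rule says, and the SAP is the specification against which the programming is checked.

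Applying 8.1 to the sarcoidosis tables is an inference. It is a reasonable one, since 8.2 offers no other definition, but it is not stated.

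A reader might infer that every recorded prior medication is misclassified. That is not so: the SAP deliberately counts drugs that continue into treatment as both prior and concomitant. All subjects enter on stable prednisone (Protocol 9.1, criteria 9 and 10), so such drugs are common.

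A reader might also infer that the efficacy results or the deviation reporting are compromised. The documents do not support this. The corticosteroid analysis in SAP 9.8 works from dose data, not from the concomitant label. Significant deviations are summarised separately under SAP section 6, and Protocol 10.2 has its own route for recording and escalating prohibited medication.

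A last objection concerns the remedy. Under Protocol section 10, a drug stopped between screening and Day 1 is concomitant; a rule anchored at first dose makes it prior only. This stands, and the fix must acknowledge it.

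**Conclusion.** The rule is wrong as written, at low priority. For extension entrants it places drugs stopped before the first double-blind dose in the double-blind concomitant table. For subjects who do not enter the extension its second condition is undefined. Nothing else is misclassified.

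The consequence is limited to the descriptive concomitant and concomitant-sarcoidosis medication tables. No hypothesis test, effect estimate or deviation count changes. The conclusion rests on reading the sentence literally. The sarcoidosis table is affected only if 8.1 governs 8.2.

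**What to change.** Replace the double-blind sentence in SAP 8.1 with a rule that has both bounds. A medication is concomitant in the double-blind phase if it is ongoing, or has a stop date, on or after the first double-blind dose, AND it started before the first open-label dose (as estimated in SAP 4.3). For subjects who do not enter the extension, the second bound becomes a start on or before the end of their double-blind phase and follow-up. State in SAP 8.2 that the same definition applies to sarcoidosis medications.

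Record in SAP section 13 that the concomitant period starts at first dose and not at the protocol's screening visit, so that drugs stopped between screening and Day 1 are reported as prior only.

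The cost is one reworded sentence and two short notes. No new data are needed: Protocol section 10 already requires stop dates, and SAP 15.1.2 already covers partial ones.

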8.2. Prior and Concomitant Sarcoidosis Medications

The prior and concomitant sarcoidosis medications will be summarized by preferred drug name for each treatment group and total. Concomitant sarcoidosis medications will be summarized by the double-blind and the open-label phase, respectively.

8.3. Study Treatments

Study treatments and extent of exposure summaries will be provided based on the safety population in the double-blind treatment phase and the open-label extension phase, respectively. Descriptive statistics will be provided for treatment duration, number of injections, dose reduction and justifications for dose reduction by study phases.

A listing for each study phase will be provided for drug accountability and treatment compliance, respectively.

8.3.1. Extent of Exposure

Treatment duration of double-blind treatment phase (weeks) is defined as:

$$[(\text{date of last dose at double-blind treatment phase}) - (\text{date of first dose at double-blind treatment phase}) + 1]/7.$$

Treatment duration of open-label extension phase (weeks) is defined as:

$$[(\text{date of last dose at open-label extension phase}) - (\text{date of first dose at open-label extension phase}) + 1]/7,$$

Descriptive statistics will be provided for treatment durations by treatment group and total.

8.3.2. Treatment Compliance

During each visit, the number of injections that a subject was expected to take and the number of injections that a subject actually took since previous visit until prior to the current visit will be recorded on the eCRF.

Treatment compliance (%) of double-blind treatment phase is defined as:

$$\frac{(\text{Number of injections taken during double - blind treatment phase}) \times 100}{\text{Number of injections expected to be taken during double - blind treatment phase}}$$

Treatment compliance (%) of open-label extension phase is defined as:

$$\frac{(\text{Number of injections taken during the duration open - label extension phase }) \times 100}{\text{Number of injections expected to be taken during open - label extension phase}}$$

The study drug compliance rate in the double-blind treatment phase, and compliance rate in the open-label extension phase will be summarized by treatment group using the descriptive statistics. The compliance rates will also be summarized by categories (<80, 80 to <=120, and >120).

9. Efficacy Analysis

All efficacy evaluations will be conducted using the mITT population unless otherwise specified and will be provided by treatment group for the double-blind treatment phase. Efficacy evaluations will only be summarized descriptively using the open-label safety population by treatment group and total for the open-label extension phase. All summaries and analyses will be conducted on the observed values unless otherwise specified. All efficacy data will be presented in listings based on the mITT population in the double-blind treatment phase and based on the open-label safety population in the open-label extension phase. The derived efficacy variables will be displayed in data listings as well.

Additional subgroup analyses by sex, race and ethnicity will be performed on missing imputed data as specified. Other exploratory analyses may be performed as appropriate.

9.1. Sarcoidosis Treatment Score (STS)

STS is a newly developed composite score that combines the results of PFT, chest imaging, quality of life, and changes in corticosteroid dosing. Individuals may score from - 6 to + 6. Higher scores indicate improvement. Subjects tolerating Acthar Gel (or placebo) will be categorized as Response, Partial Response, and Non Response. STS can be determined by using the assessments categories as presented in table below.

Table 1: Determining the Sarcoidosis Treatment Score

	Parameter	Improved	Unchanged	Deteriorate
Category of Assessment		+1	0	-1
PFT ^a	FVC	$\geq 5\%$	> -5% to < 5%	$\leq -5\%$
	DLCO	$\geq 5\%$	> -5% to < 5%	$\leq -5\%$
Imaging	HRCT	Improved	Unchanged	Worse
Quality of Life	King's Sarcoidosis Questionnaire (General Health)	≥ 4	> -4 to < 4	≤ -4
	Fatigue Assessment Score	≤ -4	> -4 to < 4	≥ 4
	Corticosteroid taper (dosage)	$\geq 50\%$ reduction	< 50% reduction or ≥ 5 mg increase for less than 2 weeks	≥ 5 mg increase for more than 2 weeks

^aAbsolute change of % predicted.

Subject tolerating Acthar (or placebo) will be categorized according the following scoring:

- Response is defined as scores of $\geq 3/6$ points.
- Partial Response is defined as scores of $2/6$ points or stable with corticosteroid reduction (ie, a total score of +1 due to $\geq 50\%$ reduction in corticosteroid dosage).
- Non Response is defined as scores of $\leq 1/6$ points without significant corticosteroid taper (stable or deterioration).

An STS responder is defined as a subject who has an assessed STS category of Response or Partial Response at 24 weeks (Visit 8) during double-blind treatment phase and at 48 weeks (Visit 11) during open-label phase.

The descriptive statistics for developed STS scores, number and percentage of subjects in each STS response category (response, partial response and non response) will be provided at both 24 weeks (Visit 8) and 48 weeks (Visit 11). At 24 weeks (Visit 8) during double-blind treatment phase, the proportions of STS responder (defined as response or partial response) and non-responder, and corresponding odds ratio will be calculated. The 95% confidence interval (CI) of the odds ratio will be calculated as well based on asymptotic method. Pearson's chi-square test (or Fisher's exact test if any expected count is less than 5) will be used to assess the comparability between treatment groups for the STS responder

vs. non-responder rate. At 48 weeks (Visit 11) during open-label phase, the proportions of STS responder and non-responder along with 95% CI will be provided. The 95% CI will be calculated by using the exact (Clopper-Pearson) method.

Missing STS scores will be imputed at 24 weeks (Visit 8) during double-blind treatment phase. Last observation carried forward (LOCF) method will be employed to impute missing component(s) if any component of STS is missing at the post-baseline visit during double-blind treatment phase. If there is still missing component(s) after applying LOCF imputation method, STS score will remain as missing. Subjects who do not provide data (after component level LOCF imputation) to allow classification as responders will be considered non-responders, that is, missing data will be imputed as non-responder. The same missing data imputation method will be applied to other similar efficacy endpoints in double-blind treatment phase. No imputation will be applied to the open-label extension phase. A bar plot of STS category will be provided at 24 weeks (Visit 8) during double-blind treatment phase and at 48 weeks (Visit 11) during open-label phase, respectively.

Sensitivity analyses with using only the observed data will be performed for the above analysis at 24 Weeks (visit 8) only.

Subgroup analyses by sex, race and ethnicity will be performed in similar manner as specified above on the imputed data only.

STS component scores including FVC % Predicted Score, DLCO % predicted Score, HRCT Score, King's Sarcoidosis Questionnaire (KSQ) General Health Score, Fatigue Assessment Score and Corticosteroid Taper Score will be summarized. Number and percentage of subjects in each category (Improved, Unchanged and Deteriorate) of each STS component score presented in Table 1 will be provided at 24 weeks (Visit 8) and at 48 weeks (Visit 11). Pearson's chi-square test (or Fisher's exact test if any expected count is less than 5) will be used to assess the comparability between treatment groups for each STS component at 24 Weeks (visit 8) only.

Listings of STS components and STS scores will be provided by study phases. Subjects with any missing component of STS will be indicated.

In addition, correlation analysis between STS score and each of its components and/or other assessments (e.g. Six-Minute Walk Test, Physician Global Assessment, ect.) may be performed based on the data from both study phases. Pearson or Spearman correlation coefficients and the corresponding p-values will be generated depending on the distribution

of the data. The data may also be presented in scatter plots with regression line, correlation coefficient and p-value annotated.

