4.1. Sample Size

Formal sample size calculations were not performed. The sample size is based on recent literature of comparative studies ([Gibson et al., 1996](#); [Baughman et al., 2006](#); [Judson, 2014](#)) in sarcoidosis. There are 55 subjects randomized to this study.

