4.2. Randomization, Stratification, and Blinding

An interactive telephone/web response system will be used to allocate eligible subjects to each treatment group. Subjects will be randomized according to computer-generated allocation scheme to receive either Acthar Gel 1 mL (80 U) or placebo 1 mL administered twice a week in a 1:1 ratio. Both investigators and the subjects will be blinded to the treatment assignment. A block randomization will be performed.

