- Two baselines, baseline of overall study and baseline of active treatment, have been defined. Baseline of overall study is defined as the last assessment prior to the first dose of IMP at the double-blind treatment phase. Baseline of active treatment is defined as the last assessment prior to the first dose of active treatment in either the double-blind treatment phase or the open-label extension phase. All the analysis in the open-label extension phase that involves presenting change and/or percent change from baseline will present change/percent change from both baselines.
- Summary statistics will be provided for all study variables with descriptive statistics (number of subjects, mean, standard deviation (SD), median, minimum,

and maximum) for numerical (or continuous) variables. Frequency and percentages will be calculated for categorical variables.

- Unless specified otherwise for a given analysis, all statistical tests, when applicable, will be 2-sided with a significance level of 0.05.
- All data collected will be presented in listings, sorted by treatment group, subject identifier and date/time of procedure or event, if applicable.

All analyses will be conducted using SAS® Version 9.4 or higher. The Medical Dictionary for Regulatory Activities (MedDRA) version 23.0 will be used for coding adverse events (AEs), and medical and surgical histories. Prior or concomitant medication data will be coded according to the Anatomical Therapeutic Chemical (ATC) coding scheme of the World Health Organization (WHO) Drug Dictionary (Enhanced B2 dated March 2018 version, or higher) level 2 term.

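### SAP 9.1 changes the test to Fisher in sparse tables but keeps an asymptotic odds-ratio interval, which small race and ethnicity subgroups will frequently leave undefined and which can occasionally disagree with the test

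*SAP*

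**What the plan says.** SAP 9.1 plans, at week 24, the proportions of STS responders and non-responders by arm, the odds ratio and its interval: "The 95% confidence interval (CI) of the odds ratio will be calculated as well based on asymptotic method". The test is Pearson's chi-square, or Fisher's "exact test if any expected count is less than 5". That condition governs the test only. Section 9.1 gives no exact odds-ratio interval, no continuity correction and no rule for an empty cell. It names an exact interval (Clopper-Pearson) only for the week-48 proportions.

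The same section extends the analysis: "Subgroup analyses by sex, race and ethnicity will be performed in similar manner as specified above on the imputed data only". SAP 7.1 lists seven race levels, "Race (American Indian or Alaska Native, Asian, Black or African American, Native Hawaiian or Other Pacific Islander, White, Multiple, Other", and four ethnicity levels, "Ethnicity (Hispanic or Latino, Not Hispanic or Latino, Unknown, Unreported". No minimum subgroup size or pooling rule is stated. On size, SAP 4.1 says "There are 55 subjects randomized to this study", and SAP 4.2 gives 1:1 allocation. The sample code in SAP 15.4 requests the chi-square and Fisher tests and contains no odds-ratio statement.

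**The concern.** By switching to Fisher, the SAP accepts that large-sample inference is unreliable in a sparse table. The odds-ratio interval for that table rests on the same kind of approximation and is left unchanged. Sparse tables are to be expected when 55 subjects are divided by race or ethnicity. Counting unclassifiable subjects as non-responders lowers the responder counts further and makes an empty responder cell more likely.

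Two things can then go wrong. With a zero cell the planned interval does not exist, so a p-value, possibly a significant one, is reported with no measure of precision. With small non-zero cells the interval and the p-value come from different methods and may fall on opposite sides of the significance line. At stake is the readability of the subgroup tables and any effect a reader might take from them.

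**Working it through.** The plan gives no figure to reproduce: no power, response rate or subgroup size is stated.

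**Inputs from the SAP**
- Tests "will be 2-sided with a significance level of 0.05" (4.3).
- 55 subjects allocated 1:1 (4.1, 4.2), so about 28 v 27.
- Pearson, or Fisher if any expected count is below 5; asymptotic odds-ratio interval (9.1).

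**Assumptions**
- Placebo response 10% to 50%, active response 10% to 60%, in ten rate pairs including four with equal rates.
- 2 to 25 subjects per arm within a subgroup level.
- The asymptotic interval is the usual log-odds (Woolf) one.

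**Formulas.** With responders a, c and non-responders b, d in the two arms:
- OR = ad/(bc)
- interval = exp{ln OR ± 1.96 √(1/a + 1/b + 1/c + 1/d)}
- P(undefined) = 1 − [1 − p₁ⁿ − (1−p₁)ⁿ] × [1 − p₂ᵐ − (1−p₂)ᵐ]

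**Worked tables**
- 5/10 v 0/10: smallest expected count 2.5, so Fisher, p = 0.033. The term 1/c is 1/0, so there is no asymptotic interval. The exact conditional interval is 1.20 to infinity.
- 7/10 v 2/10: smallest expected count 4.5, so Fisher, p = 0.070. OR = (7×8)/(3×2) = 9.33 and SE = √(1/7 + 1/3 + 1/2 + 1/8) = 1.049. Interval = exp(2.234 ± 2.057) = 1.2 to 73. The exact interval is 0.88 to 127.

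**Probability of a zero cell**
- 6 v 6, rates 55% v 35%: 1 − (1 − 0.0277 − 0.0083)(1 − 0.0018 − 0.0754) = 11%.
- 6 v 6, rates 60% v 20%: 30%.
- 4 v 4, same two rate pairs: 30% and 50%.
- Rates 30% v 10%: 59% at 6 v 6 and 74% at 4 v 4.

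**Enumeration of every table.** Unweighted means over the ten rate pairs and over equal and moderately unequal arms:

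| Per arm | Interval undefined, mean (range) | Excludes 1 with p > 0.05, mean (max) |
|---|---|---|
| 2–4 | 68% (23–97%) | 0% |
| 5–8 | 29% (2–83%) | 1.1% (13.2%) |
| 9–13 | 13% (0–63%) | 2.2% (16.3%) |
| 14–18 | 6.6% (0–41%) | 0.5% (4.5%) |
| 19–25 | 3.3% (0–25%) | 0.2% (4.6%) |

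The second event passes 10% only at roughly 7 to 13 per arm with a large effect. At 10 v 10 it has probability 7% (55% v 35%) and 16% (60% v 20%), but 0.01% to 2.9% under equal rates. It cannot occur in balanced tables of 4, 5, 8 or 14 per arm.

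**Full comparison, 28 v 27.** None of the 812 tables has an interval excluding 1 with p > 0.05. The interval is undefined with probability 1 − (1 − 0.9²⁸)(1 − 0.9²⁷) = 10.7% if both rates are 10%, and at most 0.4% if both are 20% or more. The opposite mismatch (interval includes 1, p ≤ 0.05) reaches at most 3.5%.

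**Check of the fix.** With the exact conditional interval, none of 12,311 Fisher-rule tables has an interval excluding 1 with Fisher p > 0.05, and zero-cell tables get a one-sided bound. The opposite mismatch can remain when the arms are unequal, because the exact interval is equal-tailed and the two-sided Fisher p-value is not. For 3/3 v 0/4, Fisher p = 1/C(7,3) = 1/35 = 0.029, but the single tail is also 0.029, above 0.025, so the exact interval includes 1.

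**The case against.** The strongest reply is that little depends on this. The study is exploratory, no sample size was formally derived, and the full comparison is essentially untouched. An undefined odds ratio in a level with four per arm is visible in the output and misleads nobody, and an exact interval there would be one-sided and uninformative. All of this stands, and it limits the weight of the point. It does not supply the missing rule: 5/10 v 0/10 would still show a significant p-value with no interval.

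Two stronger readings are tempting, and the documents support neither.

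- **That the interval often excludes 1 beside a non-significant test.** The enumeration puts this at about 0 to 2% on average. The higher figures need particular arm sizes and a large assumed effect.
- **That the asymptotic interval is too narrow.** Under equal rates of 20% to 50% at 10 v 10, it excludes 1 in 0.4% to 3.9% of trials, while Fisher rejects in only 0.8% to 1.3%. The largest value over eight size pairs was 5.1%, at 12 v 10. The disagreement therefore mostly reflects Fisher's conservatism, not an interval with excess error.

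It is also fair to object that a wider choice of intervals would not help. A mid-p interval has lower limit 1.12 for 7/10 v 2/10, so it still excludes 1 beside p = 0.070. A Newcombe interval for the risk difference in that table is 0.066 to 0.740, which excludes 0.

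**Conclusion.** The point holds as a minor gap in specification. SAP 9.1 pairs Fisher's test with an asymptotic odds-ratio interval in sparse tables and carries the pairing into the subgroups. The main consequence is a missing interval in small race and ethnicity levels; the lesser one is an occasional contradiction with the adjacent p-value. Sex subgroups near half the trial (14 to 18 per arm) are little affected unless response is near 10%, and the same condition applies to the full comparison. These frequencies rest on assumed response rates and subgroup sizes. The mechanism and the two worked tables do not.

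**What to change.** Add to SAP 9.1 that, whenever the Fisher rule applies, the exact conditional 95% interval for the odds ratio replaces the asymptotic one, with a one-sided bound shown when a cell is zero. Add EXACT OR to the PROC FREQ code in SAP 15.4. A minimum size or pooling rule for race and ethnicity levels would be a useful companion, since an exact interval in a very small level carries little information. A Newcombe risk difference may be added for description but does not remove the disagreement with Fisher, and neither does mid-p.

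The cost is one sentence and one SAS statement. The exact intervals are somewhat wider and conservative, and with unequal arms an interval including 1 may still sit beside a Fisher p-value just under 0.05. A footnote can say so.
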